Rationale: In the DASH trial, sodium intake was kept constant across the three dietary patterns but varied among participants within a range of 100-174 mmol depending on total energy intake. This aim addresses the important public health question of whether a reduced fat, high fruit, vegetable, and low-fat dairy diet is effective in lowering blood pressure at levels of sodium consumption that are at or below current public health guidelines for maximal intakes. The blood pressures measured at the end of each feeding period are compared between the control and combination diets for each level of sodium intake.

We hypothesize that the combination dietary pattern will significantly reduce blood pressure relative to the control diet at each level of sodium intake.

Secondary Specific Aims

Specific Aim #3: Assess whether the effects of sodium intake on blood pressure are similar for the two dietary patterns. Specifically, assess whether the BP-effect of going from the higher to the lower levels of sodium intake differs for participants in the control and combination dietary patterns.

Rationale: The issue of whether the BP-effects of sodium reduction and the combination dietary pattern are additive is of important public health interest. Additive or synergistic (i.e., positive interaction) effects would argue for a public health campaign promoting both interventions. Similarly, it would be important to know whether an interaction effect is not additive (negative interaction). Although specific aim #2 addresses the issue of interactions indirectly, this aim provides a direct test of the additivity of these effects, and is a two-sided hypothesis.

Specific Aim #4: Determine whether the BP-effect associated with reducing sodium from the higher- to intermediate-level of intake differs from the BP-effect associated with reducing

sodium from the intermediate- to lower-level of intake. This is equivalent to testing whether the BP-effects of sodium are linear across the three sodium levels. This question is addressed both overall and separately for each dietary pattern.

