
For each individual, all blood pressure measurements (baseline, and three follow-ups) will be entered into the analysis. For the sodium analyses, results will, in effect, be based on differences between different sodium treatment levels, and so the baseline values will only contribute to the estimates of the variance components. For the diet analyses, however, the baseline values add information and improve the study power.

The fundamental strategy is to fit linear models that include the effects of interest for each specific aim, together with the other factors that are regarded as being relevant to the outcome. Parameter estimates will be determined by the method of maximum likelihood, assuming normally-distributed random terms. The baseline terms are included because they assist in estimating the between-individual component of variance, and models that incorporate this random term are more efficient than those that do not. For some secondary outcomes, such as ambulatory blood pressure, baseline values are not collected, and thus cannot be used in the analysis. While this may result in some power loss, it does not invalidate the basic modeling approach.

An essential feature of the analysis plan is to deal properly with the fact that we must expect multiple observations on the same person to be correlated. There is ample evidence of this

correlation from the original DASH study, where the correlation between two blood pressures from the same person was about 0.90, irrespective of their separation in time. This feature can be dealt with fairly easily, however, by using a mixed-effect regression analysis (also called "repeated measures analysis of variance", or "generalized least squares", or multilevel analysis (101)). Computations that were carried out for the purpose of investigating the consequences of different analysis strategies consistently showed large efficiency gains for this approach. For this reason, the "repeated measures" model is planned for all analyses. This will be implemented by including random effects for individuals in all models. The cohort effects (nested in sites) will also be considered random effects, since it is plausible that participants in the same cohort might give correlated responses.

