Corrections for multiple testing, when used, will be based on Holm's method (102). This is done by sorting the p values from smallest to largest, $p_1, ..., p_n$, then successively comparing p_i to α /(n-i+1) until the first non-rejection. This method applies in all cases where the more familiar Bonferroni method has been used to bound the overall Type I error probability at α , but it is uniformly more powerful than the latter method.

Aim #1: Blood Pressure Change due to Sodium Levels within Combination and Control Diets

For the first specific aim, the repeated measures model will be parametrized to include:

- 1. contrast of higher vs. lower sodium within the Control diet;
- 2. contrast of higher vs. intermediate sodium within the Control diet;
- 3. contrast of higher vs. lower sodium within the Combination diet;
- 4. contrast of higher vs. intermediate sodium within the Combination diet;
- 5. contrast of Combination vs. Control diet
- 6. site effects
- 7. cohort effects, nested within sites
- 8. period effects (for four feeding periods nested within a cohort);
- 9. person effects

Site effects will be considered fixed, while cohort, period, and person effects will be considered random. The assumptions underlying this approach will be investigated to determine whether the cohort and period should be considered fixed effects.

The primary analysis involves first testing 1 and 3 (higher vs. lower sodium within diet) using equal-tailed, .05-level, two-sided tests with a Holm correction for the two tests. If the first analysis yields any positive results, then 2 and 4 will be tested using the same strategy; specifically, 2 will be tested only if 1 was significant, and 4 will be tested only if 3 was significant. If there is only one test at this second stage, then it will be at .05 level; otherwise, the Holm adjustment will also be used for the two tests at the second stage. For purposes of presentation, the remaining contrast (intermediate vs. lower) will be shown, but its test is implicit in the tests already done.

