To compute power, the statistical routine that will actually do the analysis (the generalized estimating equation module of Stata) was employed. Only the design specification (fixed and random effects) is required, since given this, the results depend only on the residual variance estimate. We provide this latter value from the DASH results. This procedure provides standard deviations for each estimate, which is all that is required for power computation.

Using the DASH results to estimate variance components (between = 150 mmHg, within = 40 mm Hg), the following table gives the effect sizes that can be detected with the indicated power, allowing for multiple testing, for each of the specific aims. These computations are based on two-sided .05 (adjusted) level.

Detectable Effects: Systolic BP in mmHg

	Detectable Effect at Power =		
	70%	80%	90%
1. Sodium Effects within Diets (2)	0.8	0.9	1.0
2. Diet Effects within Sodium Levels (3)	1.2	1.3	1.5
3. Interactions (2)	1.1	1.2	1.4
4 Linearity of Sodium Effect (2)	1.4	1.5	1.7

Number of Holm adjustments in parentheses.

The results can be summarized as follows.

Aim #1. A sodium effect of 1.0 mm Hg (difference between two groups) can be detected (power = 90%) between two sodium levels, within a diet.

Aim #2: A diet effect of 1.5 mm Hg (difference between two groups) can be detected (power = 90%) between the two diets within a sodium level.

Aim #3: A diet effect on a sodium effect of 1.4 mm Hg can be detected (power = 90%). The effect here is defined by first computing a sodium effect (such as lower vs. higher) d_1 in the control diet, the same sodium effect d_2 in the combination diet, and then computing $d_2 - d_1$.

Aim #4: A departure from linearity of 1.7 mm Hg/sodium-class can be detected (power = 90%). The effect here is computed as d_1 equal to the intermediate vs. lower sodium effect, d_2 equal to the higher vs. intermediate sodium effect, and then computing d_2 - d_1 .

As Stamler et al. (5) note, a population-wide reduction of 3mm Hg in SBP could have a great public health impact. This provides a reference value suggesting that the study will have excellent power to detect meaningful effects for Aim #1-#3.

Subgroup Effects on Power

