The above figures pertain to the primary analyses for each specific aim. Analyses within subgroups will have lower detectable effect levels, but a single correction can be made in these cases, so long as the variance component estimates still pertain. Let p denote the fraction of data available for analysis (relative to complete data), and then multiply the effect sizes by $1/\sqrt{p}$. To take changes in variance into account, multiply the effect sizes by the ratio of the presumed within-person variance to the overall value of 150+40/5 that was used for the full analysis.

The following table adjusts that given previously, so that it pertains to a subgroup analysis using only half the participants – and is therefore roughly applicable for race-specific or gender-specific analyses.

DASH2 Protocol Version 1.6

FI-#J.

Detectable Effects: Systolic BP in mmHg For Half of the Entire Sample

	Detectable Effect at Power =		
	70%	80%	90%
1. Sodium Effects within Diets (2)	1.1	1.2	1.4
2. Diet Effects within Sodium Levels (3)	1.7	1.9	2.1
3. Interactions (2)	1.6	1.7	2.0
4 Linearity of Sodium Effect (2)	1.9	2.1	2.4

The following table repeats the detectable effects, now for the subgroup of hypertensives only (assumed to be 30% of the total sample), and using the with person-specific variance (91+60/5) that was observed among hypertensives in the control group in the DASH study.

Detectable Effects: Systolic BP in mmHg Hypertensives Only

	Detectable Effect at Power =		
	70%	80%	90%
1. Sodium Effects within Diets (2)	1.8	2.0	2.2
2. Diet Effects within Sodium Levels (3)	2.6	2.9	3.3
3. Interactions (2)	2.5	2.8	3.2
4 Linearity of Sodium Effect (2)	3.0	3.4	3.9

The final table is for the 70% normotensives, with person-specific variance equal to 71+37/5, again from the DASH control group of normotensives.

Detectable Effects: Systolic BP in mmHg Normotensives Only

Detectable Effect at Power -

	70%	80%	90%
1. Sodium Effects within Diets (2)	0.9	1.0	1.1
2. Diet Effects within Sodium Levels (3)	1.4	1.5	1.7
3. Interactions (2)	1.3	1.4	1.6
4 Linearity of Sodium Effect (2)	1.6	1.7	2.0

16. Quality Control and Data Management

Principles and Philosophy

The objective of quality control efforts is to ensure that project data and activities are standardized, accurate, and timely, thus minimizing variation not associated with treatment effects. To achieve this, staff are trained and certified rigorously and all trial activities are monitored routinely.

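### The single person effect gives every sodium contrast the same variance, and section 15 names a different estimator, so the higher-vs-lower standard error may be too small

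*Protocol*

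**What the plan says.** Protocol section 14 (Data Analysis, Design) plans a repeated-measures model for all analyses, fitted by maximum likelihood with normal random terms. Correlation within a person is handled as follows: "This will be implemented by including random effects for individuals in all models". Under Aim #1, "Site effects will be considered fixed, while cohort, period, and person effects will be considered random". Period is nested within cohort, so it is not person-specific. The one planned check of assumptions is: "The assumptions underlying this approach will be investigated to determine whether the cohort and period should be considered fixed effects". No person-by-sodium term, unstructured covariance or robust variance is named.

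The same section justifies the model by reporting that in DASH "the correlation between two blood pressures from the same person was about 0.90, irrespective of their separation in time". It does not say whether this refers to single days or to means over several days.

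Section 15 names the routine that will do the analysis as "the generalized estimating equation module of Stata". For the inputs it says: "Using the DASH results to estimate variance components (between = 150 mmHg, within = 40 mm Hg". Under Subgroup Effects on Power it refers to "the overall value of 150+40/5 that was used for the full analysis". The DASH source had no within-person sodium contrast; section 2 (Specific Aim #2, Rationale) says: "In the DASH trial, sodium intake was kept constant across the three dietary patterns".

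**The concern.** A single person effect implies that the higher-lower, higher-intermediate and intermediate-lower differences all have the same variance. That is hard to square with the protocol's own argument that salt response differs by race, sex, hypertension status, age and renin (sections 2 and 3). Table 5 adds to the spread: the higher-lower gap is 80 mmol at 1600 Kcal and 160 mmol at 3600 Kcal. If response varies between people, the widest contrast varies most, and a pooled residual understates its standard error.

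Higher vs lower within each diet is the first-stage primary test and decides whether higher vs intermediate is tested at all. Its error rate and interval width therefore matter most.

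The conflict over the estimator makes this harder to settle. A GEE does not fit random cohort, period and person effects, and its standard errors may be model-based or robust. Robust errors would largely cure the problem, but the protocol does not say which will be used.

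**Working it through.** **Reproducing the printed table.** Inputs from section 15: between-person variance B = 150, residual W = 40/5 = 8, n = 200 per diet, two-sided 0.05 with Holm correction for m tests. The detectable effect is (z for 1 − 0.05/(2m), plus z for power) × SE. The squared SEs are:
- sodium: 2W/n
- diet: 2(B+W)(1−ρ²)/n, with ρ = B/(B+W)
- interaction: 4W/n
- linearity: 6W/n

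Aim 1 at 90% power: (2.241 + 1.282) × √(16/200) = 0.996, printed as 1.0. The other 90% values are 1.45, 1.41 and 1.73, printed as 1.5, 1.4 and 1.7. All 12 cells match after rounding, so the table contains no person-by-sodium or person-by-period variance.

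**How much response variation the protocol implies.** Section 3 (The Dose-Response Effect) cites 6.0 mm Hg per 100 mmol in hypertensives and 2.3 in non-hypertensives, that is 3.0 and 1.15 per 50 mmol. With the 30/70 mix of section 6, the SD from hypertension status alone is √(0.3 × 0.7) × (3.0 − 1.15) = 0.85. The documents give no total figure; SDs of 1 and 2 are assumptions.

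**Effect on the standard errors.** Let v be the variance of a person's linear response per sodium level. Per person, the true variances are 16 + 4v (higher-lower), 16 + v (each adjacent difference) and 48 (linearity, where a linear slope cancels). From the three follow-ups, the model applies the average, 16 + 2v, to every difference, and hence 48 + 6v to linearity.

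| Response SD | v | Model/true SE, higher-lower | True size at 2.5% | at 5% | Linearity at 5% |
|---|---|---|---|---|---|
| 0.85 | 0.72 | √(17.44/18.87) = 0.96 | 3.1% | 6.0% | 4.1% |
| 1 | 1 | √(18/20) = 0.95 | 3.3% | 6.3% | 3.8% |
| 2 | 4 | √(24/32) = 0.87 | 5.2% | 9.0% | 1.6% |

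In simulations with baseline as a fourth measure, the 2.5% test had size 4.3–5.3% at v = 2 and 5.4–6.7% at v = 4, depending on where baseline sits on the sodium scale.

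**Independent person-by-period variation.** With 8 added to the residual, simulation gave a true SE of 0.40, a mean model SE of 0.40 and 2.7% rejection at nominal 2.5%. The estimated residual absorbs it.

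**Diet tests.** Baseline averages three screening days and two run-in days (section 12). Suppose follow-ups correlate 0.95 with each other but 0.90 with baseline; both values are assumptions. The pooled correlation is 0.925. The model's variance factor is 1 − 0.925² = 0.144, and the true factor is 1 − 2(0.925)(0.90) + 0.925² = 0.191. A .0167 test then has size about .037.

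**The correlation.** 150/158 = 0.95 for five-day means and 150/190 = 0.79 for single days; neither is 0.90. The subgroup components give 91/(91 + 60/5) = 0.88 and 71/(71 + 37/5) = 0.91, with residuals of 12 and 7.4. Weighted 30/70, B = 77, W = 8.8 and the correlation is 0.90; the Aim 1 effect at 90% power is 3.523 × √(2 × 8.78/200) = 1.04. If instead 0.90 is imposed on a total of 158, W = 15.8 and the effect is 1.40; with B held at 150, W = 16.7 and it is 1.44.

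**The case against.** The exact covariance structure is often left to a statistical analysis plan, and the wording on random effects for individuals does not strictly exclude a random sodium slope. Both points are fair. But section 14 lists the model terms one by one, includes only person effects at that level, and limits its check to cohort and period. The conflict with section 15 lies within the protocol itself.

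The spread of salt response beyond 0.85 is not in the documents, so the upper sizes are conditional. The lower baseline correlation is also an assumption, and the statement that correlation does not depend on separation in time points the other way. These objections limit the size of the effect without removing its direction.

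A reader might infer three stronger things, which the documents do not support:
- That the standard errors leave out all extra within-person variation. They do not: the residual is estimated from trial data, and only unequal contrast variances cause bias.
- That the gap between 0.90 and 0.95 makes the detectable effects 40% optimistic, with power near 60% at the printed values. That holds only if the residual doubles. Sodium power depends on the residual alone, and the protocol's stratum figures give about 0.90 with an Aim 1 effect near 1.0.
- That power in non-hypertensives falls to 61% for a 1.15 mm Hg step. At correlation 0.90 on that stratum's total of 78.4, the residual is 7.84 and power is about 88%, against 90% with 37/5.

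**Conclusion.** The point holds for the standard errors and the choice of estimator. Under the model as written, the higher-vs-lower standard error would be 0.96 to 0.87 of its true value for a response SD of 0.85 to 2 mm Hg per 50 mmol. A nominal 95% interval would then cover about 94% to 91%. The linearity test errs in the conservative direction. The figures assume a residual of 8, a linear person-specific response and a normal approximation. The diet tests could be affected too, but only if baseline correlates less with follow-up than follow-ups do with each other, which the documents do not show.

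The consequence for power is small. Even at a detectable sodium effect of 1.44 mm Hg, power in the full sample at the 3 mm Hg reference of section 15 exceeds 99.9%. The 0.90 needs explaining, but it does not invalidate the Aim 1 figure.

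**What to change.** Name one estimator in both sections. Then use either:
- a likelihood model with an unstructured within-person covariance over baseline and the three sodium levels; or
- the random-intercept (exchangeable) model with person-clustered robust standard errors.

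Say how cohort and period enter under the chosen method. State whether 0.90 refers to single days or to means, reconcile it with 150 and 40, and restate the detectable effects only if the residual changes.

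The cost is wording, a few more covariance parameters (ten in a 4 × 4 matrix, with 400 people) and a somewhat larger standard error for higher vs lower. In the table's cases that is √(18.87/200) = 0.31 instead of √(17.44/200) = 0.30 at SD 0.85, and 0.40 instead of 0.35 at SD 2. No new data or participants are needed.

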For all four aims, further secondary analyses will adjust for the potentially confounding effects of race, sex, age, body mass index, education, physical activity, and alcohol intake. Interaction terms are used to determine if any observed treatment effects differ for various subgroups. Additional analyses will test whether baseline renin status influences treatment differences.

Handling of missing data.

Participants not completing the post-randomization follow-up (either due to nonattendance at data collection visits or to protocol escape levels) are likely to represent a nonrandom subset of the overall randomized population. For example, those individuals who are required to initiate antihypertensive medications are likely to be the participants who would have had the highest end-of-intervention blood pressure levels. End-of-intervention blood pressure values for such participants are discussed in section 12 (Outcomes Measures).

Because of the cross-over nature of the study design, some dropouts will not have any BP measurements for one or more sodium levels. As described in section 12, we use the average of these individuals' screening blood pressures as their end-of-intervention blood pressures. The rationale for this rule is that, in essence, these individuals are just very noncompliant with the study diets, and our best estimate of their blood pressure on their usual diets is the average of their screening blood pressures. The only exception to this rule is for those individuals who are randomized but who never start any of the intervention feeding periods. Since loss to follow-up in these individuals cannot be related to treatment assignment, they are treated as if they were never randomized and excluded from all analyses.

Finally, subject to the preceding considerations, analyses are conducted using an intention-totreat philosophy, whereby each randomized participant is included in each analysis according to his/her randomly assigned diet group.

15. Sample Size / Statistical Power

The proposed sample size of 400 participants (200 in each of the combination and control diet arms) was selected to provide adequate power, both overall and within subgroups, for addressing specific aims #1 and #2. This section summarizes power computations to address all four of its specific aims. We assume two-sided alternative hypotheses for each specific aim, and we also include allowance for multiple testing adjustment, as indicated above.

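### The planned interaction test for hypertensive status makes no provision for the unequal within-person variances the protocol itself reports; with one model-based residual variance its nominal 5% size would be about 7.5%

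*Protocol*

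**What the plan says.** Section 14 (Data Analysis, Design) plans one repeated-measures model for every analysis, estimated by maximum likelihood with normally distributed random terms. On the within-person correlation it says: "This will be implemented by including random effects for individuals in all models". After the four aims, section 14 turns to effect modification: "Interaction terms are used to determine if any observed treatment effects differ for various subgroups". It does not say that variances may differ between subgroups and does not ask for robust standard errors.

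Section 15, describing the power calculation, says that only the fixed and random effects need to be specified, "since given this, the results depend only on the residual variance estimate". It names the generalized estimating equation module of Stata as the routine that will do the analysis.

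Under Subgroup Effects on Power, section 15 gives different variances by hypertensive status. The hypertensive table, for a group "assumed to be 30% of the total sample", is described as "using the with person-specific variance (91+60/5) that was observed among hypertensives in the control group in the DASH study". The table for the other 70% is "with person-specific variance equal to 71+37/5, again from the DASH control group of normotensives".

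Hypertensive status is one of three subgroup factors named under Specific Aim #1 in section 2.

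**The concern.** The protocol expects the smaller group to have the larger within-person variance. It uses that in the separate power tables but does not carry it into the model that compares the two groups. A single pooled residual variance is dominated by the larger, less variable group, so it understates the uncertainty of the hypertensive estimate and hence of the difference. The interval for that difference would be too narrow and its p-value too small. The result could also disagree with the separately fitted subgroup estimates reported beside it. Section 14 drops multiplicity adjustment for the secondary analyses under the aims and adds none for these interaction tests, so nothing offsets the inflation.

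**Working it through.** **Inputs (Protocol section 15, with the outcome definition in section 12).** 200 participants per diet. 30% hypertensive gives 60 per diet; 70% gives 140. The outcome is the mean of five daily means. Residual variance is therefore 60/5 = 12 in hypertensives and 37/5 = 7.4 in normotensives. Between-person variances are 91 and 71.

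**Do these act as residual variances in the protocol's own tables?** For Aim #1 with two Holm tests, the detectable effect is (2.241 + z_power) × sqrt(2 × residual variance / n per diet), at 70/80/90% power:

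| Sample | Recomputed (mm Hg) | Stated (mm Hg) |
|---|---|---|
| All (40/5 = 8, n = 200) | 0.78 / 0.87 / 1.00 | 0.8 / 0.9 / 1.0 |
| Hypertensive (12, n = 60) | 1.75 / 1.95 / 2.23 | 1.8 / 2.0 / 2.2 |
| Normotensive (7.4, n = 140) | 0.90 / 1.00 / 1.145 | 0.9 / 1.0 / 1.1 |

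Agreement is within rounding or 3%, so they do.

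**Sodium contrast by hypertensive status, within one diet.**
- True SE of the difference: sqrt(2 × 12/60 + 2 × 7.4/140) = sqrt(0.400 + 0.1057) = 0.711 mm Hg.
- Pooled residual variance: 0.3 × 12 + 0.7 × 7.4 = 8.78.
- SE from the pooled model: sqrt(2 × 8.78 × (1/60 + 1/140)) = 0.647 mm Hg.
- Ratio: 0.647/0.711 = 0.909, so the SE is about 9% too small.
- Size of a nominal 5% test: 2 × (1 − Φ(1.96 × 0.909)) = 7.5%. A nominal 95% interval covers about 92.5%.

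In a simulation of 20,000 trials with three periods and person effects removed, the pooled test rejected 7.6% of the time at n = 400 and 7.5% at n = 200. A test allowing unequal variances rejected 5.3% and 5.2%. Sample size does not cure the problem.

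**Diet contrast by hypertensive status.**
- Baseline in the model: the baseline-adjusted variances are 103 − 91²/103 = 22.6 and 78.4 − 71²/78.4 = 14.1. The size is 7.4%.
- No baseline, as for 24-hour pressure but using the clinic systolic variances: the total variances are 91 + 12 = 103 and 71 + 7.4 = 78.4. The size is 6.3%.

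**Sensitivity of the sodium figure.**
- By hypertensive share: 20% gives 8.9%, 25% gives 8.2%, 35% gives 6.8%, 40% gives 6.2%, and 50% gives 5.0%.
- Assumption not in the protocol: a common period-to-period variance of 5 or 10 is added to both groups. With 5 the residuals are 17 and 12.4 and the size is 6.6%; with 10 they are 22 and 17.4 and it is 6.1%. Section 8 expects the feeding breaks to add some variability, but does not say how much or in whom.

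**The case against.** The strongest reply is that the single, model-based variance is inferred. No sentence in section 14 says that the interaction model has one residual variance, and the section 15 remark about the residual variance estimate describes a power calculation. The GEE routine named there also allows robust standard errors, which would bring the size back to about 5%. The choice might also be settled in a statistical analysis plan that is not at hand. This stands to the extent that the 7.5% must be stated conditionally. A reader might infer that the protocol commits to a test with a 7.5% error rate, and the text does not go that far. It does, however, fix one model for all analyses, add the interaction terms to it, and report figures that contradict equal variances, without providing for them.

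Two further points stand. The interaction sentence does not name hypertensive status, and the list of modifiers under Other Objectives in section 2 speaks of baseline blood pressure. The figure applies to the two-group split named under Specific Aim #1. Second, a reader might infer that the trial's claim to be powered for hypertensive status is undermined. It is not: that claim and the section 15 tables concern the groups analyzed separately, where each fit estimates its own variance.

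Finally, section 14 treats secondary analyses as interpretive, so no trial decision turns on this test. That limits the importance of the point but does not make the interval correct.

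**Conclusion.** The point holds in conditional form. If the section 14 model is fitted with one residual variance and model-based errors, the sodium-by-hypertensive-status standard error is about 9% too small and a nominal 5% test has a size of about 7.5%. The plausible range is roughly 6% to 9%.

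This assumes that the variances from the earlier DASH control group carry over, that the split is close to 30/70, and that day-to-day variation makes up the residual. The direction is stable as long as hypertensives are both the minority and the more variable group.

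The scope is the secondary test of effect modification by hypertensive status. It would be wrong to read this as a fault in the primary results: every participant receives all three sodium levels, and diet is randomized in both groups, so the full-sample contrasts are not affected. The separate hypertensive and non-hypertensive fits are not affected either.

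**What to change.** Add one sentence to section 14: models testing effect modification by hypertensive status let the residual and person variances differ by that status, or use person-clustered robust standard errors. Where baseline blood pressure is a continuous modifier, the robust option applies directly.

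The difference between the two separately fitted estimates, with SE = sqrt(SE₁² + SE₂²), is a useful check but only an approximate one, because the two subgroups share cohort and period effects.

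The cost is one or two extra variance parameters and an interaction standard error about 10% larger on the planning figures (0.711 against 0.647 mm Hg), with a corresponding loss of apparent power for this test. No new data are needed and the primary analysis does not change.
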